3.5.3 Sensitivity analyses

For the intention-to-treat population, sensitivity analyses will be made on the primary and secondary end points using worst case and/or multiple imputations. In addition, the analysis of the primary and secondary end points will be replicated in the per protocol population.

3.6 Subgroup analyses

Several analyses will be run by subgroups, as follows:

[figure not shown]
Subgroup	End point
Age <75 ≥75 years	Primary and secondary end points
Sex Women Men	Primary and secondary end points
COPD severity FEV ₁ ≥80% 50% ≤FEV ₁ <80% 30% ≤FEV ₁ <50% FEV ₁ <30%	Primary and secondary end points
Hospital size <300 beds ≥300 beds	Primary and secondary end points
Season	Primary and secondary end points

Autumn	
Winter	
Spring	
Summer	

FEV₁: volumen espiratorio máximo en el primer segundo.

4. POPULATION TO BE ANALYZED

4.1 Flow diagram

4.2 Definition of populations

4.2.1 Global included population

All included patients having a free and informed written consent adjudicated as conform.

4.2.2 Randomized population

All randomized patients. Following the intention-to-treat principle, patients will be analyzed according to the strategy assigned by the randomization.

4.2.3 Per-protocol population

All randomized patients without any major protocol deviation. The major protocol deviations were pre-specified prior to unblinding treatment codes and database lock for analyses. (Cf. table in section 7).

4.3 Populations used in analyses

The populations for statistical analysis will be:

Population	Analysis
Global set	Descriptive purpose (study inclusion flowchart)
Randomized set	With intention to treat principle: Demography and clinical characteristics at baseline All analyses With 'as-treated' principle: Safety analyses
Per protocol set	Sensitivity analyses

5. DATA REVIEW

5.1 General considerations

- The investigator completes patient's data in an electronic Case Report Form (**eCRF**).
- The Clinical Research Associate (**CRA**) visualizes the data remotely.
- Data management and queries will be done under the responsibility of SH Medical.
- Moreover, a data-management plan, written jointly by the data-manager, the coordinating investigator, the scientific director and the statistician, will be implemented.
- After correcting the errors shown after data-management plan implementation, a data review meeting will be held to validate the entire database with the investigator.
- The database will be frozen for statistical analysis.
- The statistical analyses will be done by the personnel of the Biostatistics Department at Ramón y Cajal Hospital in charge of the study.

5.2 Blind review

In order to ensure the smooth progress of the blind review meeting, some descriptions of the data will be done:

- Missing data on variables and consistencies.
- Chronological order.
- “Hat” variables of variables of type “if yes, please specify” or “if no, please specify”.
- Missing visit.

7. PROTOCOL DEVIATIONS

Category	Excluded from
Inclusion/exclusion criteria	
Informed consent not available/not done/declined	All
Anticoagulant therapy at the time of hospital admission	All
Other exclusion criteria violated	PPS
COPD not objectively confirmed	PPS
Management strategies	
Randomization more than 24 hours after admission	PPS
D-dimer testing more than 24 hours after randomization	PPS
Missing CT pulmonary angiogram in patients with a positive D-dimer (intervention group)	PPS
End points	
Missing data on primary end points	PPS
Missing data on secondary end points	PPS

PPS: leading to the exclusion from the per-protocol population analysis.

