2.10 Statistical plan

Statistical design

SLICE is an investigator-initiated, phase III, prospective, international, multicenter, randomized (1:1), open-label with blind end-point evaluation, parallel-group trial comparing the efficacy and safety of an active search for PE (intervention group) with usual care (control group) in patients with unexplained exacerbations of COPD who require hospital admission

Null and alternative hypotheses

The primary aim of the trial is to demonstrate superiority in the intent-to-treat analysis of an active search for PE over usual care with regard to primary end point as the composite of death from any cause, non-fatal (recurrent) symptomatic VTE, or readmission for COPD exacerbation within 90 days after enrollment (90daycomposite).

The null and alternative hypotheses are as follows:

$$H_0: 90\text{daycomposite}_{\text{intervention}} = 90\text{daycomposite}_{\text{control}}$$

$$H_1: 90\text{daycomposite}_{\text{intervention}} \neq 90\text{daycomposite}_{\text{control}}$$

Analyses

The intention-to-treat (**ITT**) analysis dataset will be the source of data for all analyses. This will include all randomized participants regardless of actual receipt or compliance with the intervention. Safety analyses will also be performed in the safety analysis set, which will consist of all participant who receive D-dimer testing. In addition, a per-protocol (**PP**) analysis of all patients randomized and managed without major protocol violations/ deviations will be carried out; this dataset will support sensitivity analyses to complement the primary ITT analyses.

Protocol deviations (minor) refer to incidents involving non-compliance with the protocol that are unlikely to have a significant impact on the

participant's rights, safety or welfare, or on data integrity. Examples of deviations include forgetting to complete a procedure at a specified visit or a patient receiving an inadequate management strategy.

Protocol violations (major) refer to more serious incidents involving non-compliance with the protocol that may result in significant effect on the participant's rights, safety, or welfare or data integrity. Protocol violations could result in the participant being excluded from the eligibility analysis and/or result in the participant being discontinued from the trial. Examples of violations include non-compliance with inclusion/exclusion criteria or inadequate risk classification.

Efficacy analyses

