means that a causal relationship between a study medication and an AE is at least a reasonable possibility, i.e., the relationship cannot be ruled out.

All cases judged by either the reporting medically qualified professional or the sponsor as having a reasonable suspected causal relationship to the study medication/procedure qualify as adverse reactions.

Serious adverse event: an event that fulfils one or more of the following criteria:

- Fatal.
- Immediately life-threatening.
- Results in persistent or significant disability/incapacity.
- Requires or prolongs in-patient hospitalization.
- Is a congenital anomaly/birth defect.
- Any other reason representing a significant hazard comparable to the criteria mentioned above.

Serious adverse reaction (SAR): an adverse event (expected or unexpected) that is both serious and, in the opinion of the reporting investigator, believed with reasonable probability to be due to one of the study treatments, based on the information provided.

Suspected unexpected serious adverse reaction (SUSAR): a serious adverse reaction, the nature or severity of which is not consistent with the applicable product information (e.g. Investigator's Brochure for an unapproved investigational product or summary of product characteristics for an approved product).

Length of hospital stay: defined as the interval (in days) from diagnosis of PE at the emergency department to discharge (i.e., date of discharge minus date of diagnosis).

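### SAP section 7 lets missing data on one end point remove a patient from the whole per-protocol set, so patients with a known composite outcome drop out of the per-protocol analysis of the composite

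*SAP*

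**What the plan says.** The table in SAP section 7 has two rows under its end-point category, "Missing data on primary end points" and "Missing data on secondary end points". Both carry the code PPS, which the footnote explains: "PPS: leading to the exclusion from the per-protocol population analysis". Neither row is limited to the end point that is missing.

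SAP 4.2.3 points to that table and defines a single population: "All randomized patients without any major protocol deviation". SAP 3.5.3 then states that "the analysis of the primary and secondary end points will be replicated in the per protocol population". The protocol (2.10, Analyses) gives the set its role: "this dataset will support sensitivity analyses to complement the primary ITT analyses".

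The primary end points in SAP 2.5.2 are two: the 90-day composite of death, symptomatic VTE or COPD readmission, and 90-day major bleeding. The secondary end points in SAP 2.5.4 are the three components of the composite taken singly, length of stay, clinically relevant non-major bleeding and serious adverse events.

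**The concern.** A per-protocol analysis asks what the comparison looks like among eligible patients who were managed as the protocol intended. Missing outcome data are a different matter, which SAP 3.2 and 3.5.3 already address by analysing evaluable patients and by worst-case or multiple-imputation analyses. The two end-point rows mix the two. They restrict the per-protocol set to patients complete on every end point at once, a property determined after randomization.

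For the composite this discards usable information. The composite is settled as soon as one component is observed, whatever else is missing later. A patient can also have full follow-up for all three components and still lack a discharge date or a non-major bleeding assessment. If such gaps are more common among patients with events, and more so in one arm, the per-protocol estimate is biased. The trial is open-label, so unequal completeness is conceivable, but the documents do not report it.

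**Working it through.** **Step 1: which patients the rows remove.**

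| Patient | Composite | Removed by |
|---|---|---|
| Full 90-day follow-up for the composite and major bleeding; non-major bleeding record or discharge date missing | Known | Secondary row only |
| COPD readmission on day 20, withdraws on day 40 | Known (event) | Primary row (90-day major bleeding unknown) and secondary row |
| Lost on day 40 with no event | Unknown | Both rows, but could not be counted as observed for the composite in any case |

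The first two are the problem. The second shows that deleting the secondary row alone is not enough, because the primary row also covers major bleeding.

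**Step 2: reproduce the plan's sample size.** Inputs (SAP 2.2 and 3.5.2): 40% against 30%, two-sided alpha 0.05, power 80%. With p̄ = 0.35:

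n = [1.960·√(2·0.35·0.65) + 0.842·√(0.40·0.60 + 0.30·0.70)]² / 0.10² ≈ 356 per group (unpooled variance: 353.2). The plan states 355. For 5% loss, 355/0.95 = 373.7 and 355 × 1.05 = 372.75; the plan states 373. Both figures reproduce within rounding.

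**Step 3: loss of precision.** Take 355 per group with a known composite and remove a fraction m in each group for a missing secondary end point. The documents give no value for m, so the range is an assumption. Power = Φ{[0.10·√n − 1.960·√(2·0.35·0.65)] / √(0.40·0.60 + 0.30·0.70)}, before any other per-protocol exclusion.

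| m | Removed per group | n left | Power |
|---|---|---|---|
| 0% | 0 | 355 | 79.9% |
| 2% | 7 | 348 | 79.1% |
| 5% | 18 | 337 | 77.8% |
| 10% | 35 | 320 | 75.7% |
| 20% | 71 | 284 | 70.6% |

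**Step 4: selective removal, equal in both arms.** If a fraction e of event patients and no others are removed, the risk p becomes p(1−e) / [p(1−e) + (1−p)]. With e = 10%:

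- control: 0.36 / 0.96 = 37.5%
- intervention: 0.27 / 0.97 = 27.8%
- relative risk 0.742 against 0.750; difference 9.7 points against 10

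If 2% of non-event patients are removed as well, the relative risk is 0.744.

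**Step 5: selective removal, unequal between arms (assumed 15% and 5% of event patients).**

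| Event patients removed, intervention / control | True RR 1.00 (40% in both arms) | True RR 0.75 |
|---|---|---|
| 15% / 5% | 36.2% / 38.8% = 0.933 | 26.7% / 38.8% = 0.689 |
| 5% / 15% | 38.8% / 36.2% = 1.072 | 28.9% / 36.2% = 0.800 |

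Only this imbalance moves the estimate materially, and it can do so in either direction.

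**The case against.** Several objections stand.

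- **The affected analysis is supportive.** A reader might infer that sensitivity analysis of the primary end point is compromised as a whole. It is not: the worst-case and multiple-imputation analyses use the intention-to-treat population and do not depend on section 7's per-protocol exclusions.
- **The protocol is not plainly contradicted.** Protocol 2.10 says "Examples of deviations include forgetting to complete a procedure at a specified visit" and classes these as minor. The same section also defines major violations by possible effects on data integrity, which missing end-point data could meet, and a forgotten procedure need not leave an end point missing.
- **The rows may have been meant end point by end point.** That would explain why there are two of them. The text does not say so, and the single population in SAP 4.2.3 points the other way.

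Three stronger readings are tempting but unsupported.

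- **Early deaths are removed.** This would need a site to leave the discharge date blank after an in-hospital death. Protocol 3.3 defines discharge as the end of hospitalization, and nothing makes an outcome missing because the patient died.
- **The rule empties the trial.** SAP 2.5.6 computes length of stay as "date of discharge minus date of diagnosis", the diagnosis being PE, so read literally a patient without PE has no value. That looks like a drafting slip in another section, and a value that is undefined is not clearly missing data.
- **The arm difference shifts by 1.2 to 3.7 points.** Removing 2% to 5% of one arm gives (0.40 − 0.02)/0.98 = 38.8% at the small end and (0.30 − 0.05)/0.95 = 26.3% at the large end. The arithmetic is right, but it needs every removed patient to have had an event and removal in one arm only. The documents give no basis for either assumption.

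**Conclusion.** The concern holds for the per-protocol analysis of the composite. On the natural reading of SAP section 7 with 4.2.3 and 3.5.3, patients with a known composite outcome are excluded from it because a different end point is missing. This selects on data completeness rather than adherence.

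The size cannot be taken from the documents. They give 3% observed and 5% anticipated loss to follow-up, but no rate of missing secondary data among patients whose composite is known. Under the assumed rates above, removal that is similar in both arms costs a little power and leaves the relative risk almost unchanged. Unequal removal of event patients could bias it noticeably, but nothing documented shows that this will happen. The rule should be corrected because it adds avoidable selection with no gain, not because the trial's main conclusion is at risk.

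**What to change.** In SAP section 7, delete the row on missing secondary end-point data as a reason to leave the per-protocol set. Replace the row on missing primary end-point data with an end-point-specific rule, for example: *Per-protocol membership depends on eligibility and management only. A patient with missing data for an end point is left out of the per-protocol analysis of that end point alone, and stays in the analysis of the composite whenever the composite outcome is known.* State when the composite counts as known, and use the same rule as in the main intention-to-treat analysis, so that the two analyses differ only by adherence and eligibility.

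As a separate matter, correct the start point of length of stay in SAP 2.5.6 so that it is defined for every randomized patient.

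The cost is a short SAP edit before database lock. It needs no new data and leaves the primary analysis and the sample size unchanged.
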